1.1. Background

Chronic rhinosinusitis (CRS) is defined by persistent sinonasal symptoms (nasal obstruction, facial pressure, nasal discharge, hyposmia) lasting at least 12 weeks and by objective findings of paranasal sinus inflammation.¹ CRS with nasal polypsis (CRSwNP) represents a subset of CRS defined by the above criteria along with the presence of nasal polyps in the middle meatus and has a variety of underlying causes.² Overall, cases CRSwNP respond well to endoscopic sinus surgery (ESS) with improvement in quality of life, symptom scores and endoscopic appearance.³ However, surgical treatment of the frontal sinus has been shown to be more challenging with higher rates of recurrent sinus disease. Factors associated with failure of frontal sinus ESS include advanced disease at presentation, prior ESS, inflammation or scarring in the frontal recess, middle turbinate lateralization, size of frontal sinusotomy and retained/residual frontal recess cells.^{4,5,6} Given these findings, meticulous surgical planning and removal of all obstructing bony partitions and diseased mucosa within the frontal sinus is advocated.

Additionally, in an attempt to decrease frontal sinus ESS failure, many methods of improving post-operative healing such as nasal saline and/or corticosteroid irrigations, oral corticosteroids, sinus stents, and more recently steroid releasing or impregnated stents/dressings have been used.^{2,7-10} Of these approaches, there are only 2 Food and Drug Administration approved steroid releasing sinus implants used at the frontal sinus opening (FSO).¹¹ It has been shown in a randomized controlled trial that steroid releasing sinus implants can improve both subjective and objective outcomes after endoscopic frontal sinus surgery compared to controls.¹¹ However, to date there has been no comparison of steroid releasing frontal sinus implants vs. other means of direct steroid delivery to the FSO after ESS, such as via a steroid impregnated dressing. Presently both stents and dressings are used routinely after ESS, but typically any one patient would get one or the other treatment for each of their sinuses.

The present study was designed to evaluate and compare the surgical outcomes of frontal sinusotomy and placement of a steroid releasing implant vs. a steroid impregnated nasal dressing within the FSO with the subject serving as their own control by receiving the stent and dressing randomly assigned to either the left or right sinus.

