2. STUDY DESIGN

2.1. Overview

This is a single center, randomized & controlled trial comparing the efficacy of the Propel mini or contour stent vs. Nasopore impregnated with triamcinolone acetonide at reducing frontal sinus opening stenosis and polypoid edema after ESS in patients with CRS with polyposis. Eligible subjects who undergo standard of care bilateral frontal sinusotomy will have each frontal sinus randomly assigned to either a Propel steroid eluting stent or a Nasopore nasal dressing impregnated with 2.5 ml of triamcinolone acetonide 40 mg/ml. The specific Propel stent will be chosen based on the shape of frontal sinus opening and best fit as decided by the operating surgeon. Patients will be reassessed on approximately post-operative day 7, 14, 30, 90 days, 6 months, and 12 months at their SOC follow-up visits. On the day 14 visit, the frontal sinus Propel stent and Nasopore will be completely removed per SOC. Video will be taken of the frontal sinus opening, and assessed for scarring/adhesions, presence of polypoid edema, frontal sinus patency, need for oral steroids or other interventions. Additionally, endoscopic scoring of frontal sinus by the above measures will be evaluated by 2 independent sinus surgeon reviewers. The reviewers will also be asked to rank the two frontal sinus openings as better, same or worse, compared to the opposite side.

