11. DATA ANALYSIS AND MONITORING

11.1. Data & Safety Monitoring Plan

I. Overview

A. This is a single center, prospective, observational, minimal risk study performed with a cohort of adult subjects undergoing frontal sinus surgery. Subjects will have SOC surgery and at the end of surgery each nostril will get a dressing or stent that provides mechanical support and also exudes a steroid to aid wound healing. Presently either dressing or stent is typically used in both sinuses at the surgeon's discretion, and this trial will put one of each in each sinus (left/right at random) to compare with each subject as their own control, whether there are noticeable differences in wound healing due to either treatment, during the post-operative course. Subjects will be followed for up to 12 months post-surgery.

B. Adherence statement. The Data and Safety Monitoring Plan (DSMP) outlined below for this study will adhere to the protocol approved by the University of Rochester Research Subjects Review Board (RSRB).

II. Adverse Events

- A. Adverse event assessment
 - a. This is a minimal risk study and there is a risk of loss of privacy and of misplacement of the stent.
 - b. Risk to privacy will be determined by whether identifying subject data had been released. This will be assessed annually.
 - c. Misplaced stent will be determined by whether the stent is correctly in the sinus when it is removed at the post-operative visit when it would normally be extracted.

- B. Adverse event reporting
 - a. Every adverse event that is reported to either the PI or study staff by the subject or other medical staff caring for the subject and which meets the above criteria, or which otherwise merit documentation in the judgement of the PI, will be documented with a description of the event along with a determination by the PI of severity and relatedness to study participation.
 - b. Adverse events will be reported annually to the RSRB as part of their Continuing Review of the study.

III. Safety Review Plan and Monitoring

A. Justification of sample size

The sample size is justified below in section 11.2

B. Safety and study progress reviews

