11.2. Sample Size Determination

Sample size is based on a non-inferiority design. Based on historical data it can be estimated that frontal sinusotomy will have a patency (success) rate of 85%. Given the lack of any known evidence to the contrary, we will assume that both the Propel mini/contour stent and the Nasopore impregnated with 2.5 mls of Kenalog 40 mg/ml placed in the FSO after ESS will result in a patency rate of 85%. Given that all prior clinical trials investigating local delivery of steroid to the FSO have utilized the Propel mini or contour stent, this will serve as our “standard therapy” group. Using an $\alpha= 0.05$, Power= 80%, and a minimum significant difference (δ) of 25%, 28 patients (56 total frontal sinus interventions) will be enrolled to be 80% sure that the upper limit of a one-sided 95% confidence interval will exclude a difference in favor of the “standard therapy” group of more than 25%. The ESS surgical procedure typically has a 1% complication rate and frontal sinusotomy failure rate of approximately 5%. Thus by ensuring subjects meet inclusion criteria a) through d) and that none of the exclusion criteria apply prior to enrollment, we would have a very low rate of screen failure, where an enrolled subject does not ultimately meet inclusion criteria e) and f). Hence enrolling 30 subjects should be sufficient to reach our statistical needs.

[figure not shown]
11.3. Planned Statistical Analysis:

Primary outcome measure: Grading by a blinded independent sinus expert as to whether the the propel sinus stent frontal sinusotomy side is better, worse or the same.

[figure not shown]
Secondary outcome measures:

1. Mucosal/polypoid edema
2. Adhesion/scarring
3. Size of frontal sinus opening
4. Visualization of the frontal sinus roof
5. Need for post-operative oral steroids
6. Need for post-operative interventions beyond normal debridement

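### Does the unexplained 25-point non-inferiority margin in section 11.2 call for a change to the plan?

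*Combined protocol and SAP*

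**What the plan says.** Section 11.2 opens with "Sample size is based on a non-inferiority design". It then gives the planning rate: "Based on historical data it can be estimated that frontal sinusotomy will have a patency (success) rate of 85" percent. The same rate is assumed for both treatments, and the stent is named as the reference because earlier trials of local steroid delivery used it. The margin and sample size are "a minimum significant difference (δ) of 25%, 28 patients (56 total frontal sinus interventions) will be enrolled". The criterion is stated as being "80% sure that the upper limit of a one-sided 95% confidence interval will exclude a difference in favor of the" reference treatment larger than the margin. Enrolment is then raised to 30.

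Elsewhere, section 2.1 says "Video will be taken of the frontal sinus opening, and assessed for scarring/adhesions, presence of polypoid edema, frontal sinus patency", with independent surgeon scoring on the same measures. Sections 5.1 and 11.3 make the better/same/worse grade the primary outcome. The readable secondary list in 11.3 includes size of the opening and visualization of the sinus roof, but not patency by name. The Background reports from a randomized trial that "steroid releasing sinus implants can improve both subjective and objective outcomes after endoscopic frontal sinus surgery compared to controls", without a figure.

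**The concern.** In a non-inferiority design the margin is the main judgement, because it fixes how large a loss the trial undertakes to exclude. Here it is 25 points on an 85% rate, so failures at the margin are 40% against 15%. Section 11.2 gives a basis for the 85% and for the choice of reference, but none for the 25.

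The 85% does not help to judge it. It is introduced as a rate for frontal sinusotomy in general, and the text does not say whether local steroid was used. The Background gives no size for the stent's benefit over control. A reader therefore cannot tell whether 25 points is smaller or larger than what the stent adds. If it were larger, a dressing that added nothing could pass.

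Patency is also the sizing endpoint without being named among the readable outcomes in 11.3, so the bound on which 11.2 rests has no stated place in the results. Section 11.1 describes the aim as seeing "whether there are noticeable differences in wound healing due to either treatment", which sits awkwardly beside so wide a tolerance.

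**Working it through.** **Inputs from section 11.2:** patency 85% on both sides, margin 25 points, one-sided 5%, power 80%, 28 patients. The treatments are compared within patients. The documents give no left-right correlation, so 0, 0.3 and 0.5 are assumed throughout.

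**1. The plan's own figure.** Treating the sides as independent, the usual formula is n = [p1(1−p1) + p2(1−p2)] × (z0.95 + z0.80)² / margin².
- The variance term is 2 × 0.85 × 0.15 = 0.255.
- n = 0.255 × (1.645 + 0.842)² / 0.0625 = 25.2, so 26 per treatment.
- Using the variance constrained to the margin (Farrington-Manning type) gives 28.2.

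The stated 28 is reproduced.

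**2. Exact paired power at 28 pairs.** All counts of discordant pairs were enumerated, with a one-sided 5% Tango bound and 85% on both sides.

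| Margin | corr. 0 | corr. 0.3 | corr. 0.5 |
|---|---|---|---|
| 25 points | 81.1% | 88.6% | 93.9% |
| 20 points | 62.5% | 73.2% | 82.7% |
| 15 points | 44.8% | 53.1% | 62.4% |

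The stated 80% holds at zero or positive correlation. The 20- and 15-point rows are illustrations; the documents propose neither.

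**3. What the criterion lets through.** The margin sits at 0.85 − 0.25 = 0.60. That is a true rate on the boundary, not an observed rate that would pass. Probability of meeting the 25-point criterion, Tango bound, 28 pairs:

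| True dressing patency (stent 85%) | corr. 0 | corr. 0.3 | corr. 0.5 |
|---|---|---|---|
| 60% | 5.3% | 4.7% | 5.2% |
| 70% | 23.4% | 26.0% | 29.4% |
| 85% | 81.1% | 88.6% | 93.9% |

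The first row is the nominal one-sided error.

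**4. What would have to be observed.** The half-width of the one-sided bound is 1.645 × √(0.255 × (1 − corr.)/28), or 15.7, 13.1 and 11.1 points at the three correlations. At correlation 0 the observed difference must be below about 25 − 15.7 = 9.3 points. On the exact Tango bound, with up to 12 discordant pairs, the largest net stent advantage that passes is 3 of 28 pairs (3/28 = 10.7 points). This happens only when there are exactly three discordant pairs and all favour the stent. With 4 to 12 discordant pairs the limit is 2 pairs (2/28 = 7.1 points) or fewer.

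**5. Cost of a narrower margin.** Pairs for 80% power with a Tango bound are 42, 33 and 28 at 20 points, and 73, 57 and 45 at 15 points, for correlations 0, 0.3 and 0.5. Only the 20-point margin at correlation 0.5 fits within the planned 28.

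**The case for a change.** The strongest case for a change is that it would be cheap. Two or three sentences in 11.2 could give the source of the 85%, say whether it was with local steroid, and explain the 25. One line in 11.3 could name patency and its paired bound. Without them, someone could report the dressing as non-inferior on patency against an unexplained tolerance. A dressing with twice the stent's failures (30% against 15%) would meet the criterion in 23% to 29% of trials.

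The factual part stands: the readable 11.2 gives no reason for the margin and does not qualify the 85%. The consequence does not follow, for four reasons.
- No readable passage attaches a declaration of non-inferiority to patency. The 23% to 29% is the chance of meeting a sizing criterion, not of a wrong primary conclusion.
- The missing line in 11.3 is one an analyst would fill without difficulty. Section 2.1 already has patency assessed, and 11.2 already states the direction, sidedness and level of the bound. Once the paired difference is reported with that bound, readers can hold it against any margin they prefer.
- Any fixed sample size loses power at a narrower margin, so the 20- and 15-point rows do not show that 25 is wrong.
- The remark in 11.1 comes from a monitoring overview, sets no threshold and does not conflict with the margin.

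**Conclusion.** No change is needed. The readable plan leaves its margin unexplained, but the sample size and power agree with it: 28.2 by the constrained-variance formula against 28 stated, and exact paired power of 81% to 94%. Meeting the criterion would not rule out a true loss of just under 25 points. Even so, a dressing truly at 60% would pass in only about 5% of trials, and the observed deficit could not exceed about 11 points. The primary better/same/worse grade is unaffected. Writing out a rationale would change no result. Narrowing the margin is a trade-off that would need up to 42 pairs at 20 points or 73 at 15.

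The exact figures rest on 85% patency for the stent, a Tango bound and assumed left-right correlations of 0 to 0.5; a negative correlation would lower the power. Confidence is moderate, because one figure after 11.2 and another within 11.3 are not shown and may contain a rationale or an analysis description.

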2.2. Rationale for Study Design

Steroid impregnated bioabsorbable implants can reduce scarring and inflammation post-operatively in the ethmoid cavity. Recent studies have also shown that an FDA approved bioabsorbable steroid releasing implant placed in the frontal sinus after endoscopic sinus surgery can improve surgical outcomes. However, no study to date has compared different methods of steroid delivery to the frontal sinus after endoscopic sinus surgery. Our study will add to the limited data in the literature regarding the efficacy of steroid eluting implants placed in the frontal sinus opening after endoscopic sinus surgery and provide a direct comparison of two established steroid delivery methods. Patients will serve as their own control in order to provide a direct comparison between both steroid delivery systems while limiting bias from interpatient variability.

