6. SUBJECT WITHDRAWALS

Subjects will be advised in the written informed consent forms that they have the right to withdraw from the study at any time without prejudice. Subjects will be withdrawn from the research without their consent by the investigator if they no longer qualify for the inclusion/exclusion criteria, are non-compliant (miss required scheduled study visits precluding analysis), or if the investigator determines that it is in the best interest of the subject. There are no additional study activities requiring completion prior to subject withdrawal from the study. Subjects withdrawn from the study will not be replaced.

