7.4. Subject Enrollment/Randomization

Subjects will be enrolled on the basis of the inclusion and exclusion criteria and signed informed consent. Subjects will be randomized using the envelope method to have either the Bioabsorbable steroid releasing stent placed or Nasopore soaked with 2.5 ml of triamcinolone acetonide 40 mg/ml placed in the left frontal sinus opening. The right frontal sinus opening will

have the other device placed. Patients will serve as their own comparison group and as such there will be a 1:1 ratio of frontal sinus openings treated with each method.

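### Does section 11.2 need a stated side-to-side discordance before its 80% power for 28 patients can stand?

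*Combined protocol and SAP*

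**What the plan says.** Section 11.2 opens with "Sample size is based on a non-inferiority design". It takes 85% patency from historical data and assumes that rate for both the stent and the dressing. It sets alpha at 0.05 with a one-sided 95% limit, power at 80% and a margin of 25 percentage points, and concludes that "28 patients (56 total frontal sinus interventions) will be enrolled to be 80% sure that the upper limit of a one-sided 95% confidence interval" will rule out a larger deficit against the stent. It then cites a surgical complication rate of 1% and a sinusotomy failure rate of about 5%, and settles on enrolling 30. Section 3.1 also gives 30.

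The design is paired. Section 7.4 randomises the left side and gives the right side the other product: "Patients will serve as their own comparison group and as such there will be a 1:1 ratio of frontal sinus openings treated with each method". Section 2.2 gives the reason: "Patients will serve as their own control in order to provide a direct comparison between both steroid delivery systems". Section 6 adds that "Subjects withdrawn from the study will not be replaced".

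The readable text of 11.2 and 11.3 gives no discordant proportion or within-patient correlation, names no formula, and does not say in words that the interval is paired. A figure beside 11.2 and another within 11.3 are not shown, so these absences can be asserted only for the readable text.

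**The concern.** For a paired binary outcome, the variance of the difference in proportions is governed by the discordant pairs, that is, patients with one side patent and the other not. Two marginal rates of 85% do not fix that proportion. A power statement giving only the marginal rates, the margin and alpha is therefore incomplete for this design, and the inputs look like those of a comparison between two independent groups of 28.

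Three things could be at stake. The 80% might not be the power of the trial as designed. The number of lost pairs the trial can absorb, with no replacement of withdrawals, depends on the unstated quantity. And a reader following 11.2 literally might compare 28 sinuses with 28 sinuses as if they came from different patients, giving up some of the precision that section 2.2 claims for the design.

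**Working it through.** **Inputs, all from 11.2:** patency 0.85 on each side (true difference 0), margin 0.25, one-sided alpha 0.05 (z = 1.645), power 80% (z = 0.842), 28 patients, 30 enrolled. The discordance is not given, so it is varied below over its possible range.

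**Step 1: reproduce 28.**
- Two independent groups, unpooled variance: n = (1.645 + 0.842)² × 2 × 0.85 × 0.15 / 0.25² = 6.18 × 0.255 / 0.0625 = 25.2, so 26 per group.
- Two independent groups, score variance (Farrington-Manning, restricted rates 0.915 and 0.665): 28.2 per group, with 79.8% power at 28.
- Alternatives that do not fit: one-sided 0.025 gives 33; a continuity correction gives 32.7; superiority of 85% over 60% gives 39 (one-sided) or 49 (two-sided).

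So 28 is consistent with the stated inputs, most closely under the score formula. Dividing by 1 − 0.06 for the two surgical losses gives 28 / 0.94 = 29.8, which is the 30 enrolled.

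**Step 2: the paired version.** Write ψ for the discordant proportion and φ for the within-patient correlation. With 85% on both sides, ψ = 2 × 0.85 × 0.15 × (1 − φ) = 0.255(1 − φ). The normal approximation is n = ψ × 6.18 / 0.0625.
- φ = 0: ψ = 0.255, n = 25.2. This equals the unpooled independent-group result, so the plan's figure is also close to a paired calculation that takes the sides as independent.
- Upper bound: each side fails in 15% of patients, so at most 15% + 15% = 30% can be discordant. That gives φ = 1 − 0.30/0.255 = −0.18 and n = 29.7, or 30.

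**Step 3: exact power.** Enumerating all outcomes of the paired multinomial and applying the one-sided 5% Tango score test against the 25-point margin:

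| φ (assumed) | Discordance | Power, 28 pairs | Power, 30 pairs |
|---|---|---|---|
| −0.18 (lowest possible) | 30.0% | 76.9% | 78.7% |
| 0 | 25.5% | 81.1% | 83.0% |
| 0.3 | 17.9% | 88.6% | 90.7% |
| 0.5 | 12.8% | 93.9% | 95.5% |

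A paired Wald interval gives 83.0% at 28 pairs with φ = 0, and 77.9% at the bound.

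**Step 4: lost pairs.** No document gives a loss rate after randomisation. If only 24 pairs were evaluable (an assumption: six of 30, or 20%), Tango power would be 74.6% at φ = 0, 84.9% at 0.3 and 91.4% at 0.5.

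**The case for a change.** The best case for a change is that it costs only a sentence or two. A stated discordance would make the 80% checkable, and naming a paired interval would close off an unpaired analysis. If sides were positively correlated, an unpaired interval at 28 pairs would have about 85–86% power instead of 89% at φ = 0.3, and about 89–90% instead of 94% at φ = 0.5. The missing assumption also decides whether a loss down to 24 pairs leaves 75% or 91% power.

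What stands is that the readable text omits the assumption. The rest carries less weight. The documents contain no discordance estimate, so any figure written in would itself be an unsourced assumption, and none in the possible range would change the enrolment. Nothing readable plans an unpaired analysis: sections 2.1, 2.2, 5.1, 7.4 and 11.1 all describe a side-to-side comparison within the patient. Even if an unpaired interval were used, it would be too wide under positive correlation. It would err against declaring non-inferiority, at a cost of roughly 3 to 5 points of power. Loss of pairs over 12 months is a question about the attrition allowance, not about discordance.

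The sample size is built on patency while the primary outcome in 11.3 is a better/worse/same grade. That is a separate matter; 11.2 already words its power in terms of patency.

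**Conclusion.** No change to the plan follows. The readable text of 11.2 omits the side-to-side discordance, but no stated figure is shown to be wrong. The 28 patients and 80% power fit the stated inputs, either as an independent-group score calculation or, approximately, as a paired calculation with independent sides. Because discordance is capped at 30%, exact Tango power lies at or above 77% with 28 pairs and 79% with 30. It exceeds 80% at both sizes once the sides are independent or positively correlated. Positive correlation between two sinuses of one patient is the more plausible case, but that is an assumption, since the documents give no figure. The choice of a paired interval is a detail that analysts of a design described throughout as within-patient would fill sensibly.

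This rests on the plan's own 85% patency on each side and its 25-point margin, neither of which is tested here, and on the readable text only.

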5.1. Efficacy Assessments

Efficacy will be determined by comparing the right and left frontal sinus opening after removal of the stent and dressing on POD 14, and then around day 30, 90, 6 month and 12 months. The frontal sinus opening will be assessed with a rigid endoscope, using 30, 45 and/or 70 degree scopes as necessary. Our primary efficacy outcome will be a grade assigned by 2 blinded, independent sinus surgeon experts as: better, worse or same, comparing overall appearance of the study subject's frontal sinus openings after implant removal.

Additionally, the frontal sinus opening will also be graded on an adhesion/scarring scale, a polypoid edema scale, size in mm of the opening as measured by a visual analog scale/comparison to 4 mm suction, and visualization of the roof of the frontal sinus.

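### The primary grade is relative and patency, the quantity the trial was sized on, is not a listed outcome, so 'same' does not separate both open from both closed

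*Combined protocol and SAP*

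**What the plan says.** Every statement of the primary grade sets one side against the other in the same patient. Section 11.3 gives it as "Grading by a blinded independent sinus expert as to whether the the propel sinus stent frontal sinusotomy side is better, worse or the same". Section 5.1 has two blinded experts grade "better, worse or same, comparing overall appearance of the study" subject's two openings, and section 2.1 asks them to "rank the two frontal sinus openings as better, same or worse, compared to the opposite side". Nothing in the readable text ties 'same' to an open sinus.

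The aim and the sample size are absolute. Section 2.1 compares the two products "at reducing frontal sinus opening stenosis and polypoid edema after ESS in patients with CRS with polyposis". Section 11.2 declares a non-inferiority design, and its assumption begins "we will assume that both the Propel mini/contour stent and the Nasopore impregnated with 2.5 mls of Kenalog 40 mg/ml" and assigns both a patency rate of 85%. It sets a 25-point margin, a one-sided 95% confidence limit, 80% power and 28 patients, with 30 enrolled.

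Patency is collected: under section 2.1 the video is "assessed for scarring/adhesions, presence of polypoid edema, frontal sinus patency, need for oral steroids or other interventions". The six secondary outcomes in 11.3 are edema, scarring, opening size, view of the frontal roof, oral steroid need and further interventions. Patency is not among them.

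Section 5.1 compares the sides "after removal of the stent and dressing on POD 14, and then around day 30, 90, 6 month and 12 months". No visit is named as primary.

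**The concern.** Non-inferiority on patency is a statement about how many openings stay open on each side. A better/worse/same grade does not carry that information. Two open sinuses and two closed sinuses can both be graded 'same', and the grade alone cannot tell a reader which occurred.

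The design makes joint outcomes plausible. Frontal disease is bilateral by entry criterion (section 3.2). Both sides share the patient's oral steroids, irrigation and any nasal spray (section 5), and no side goes without an active device.

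Two things are at stake. The 25-point margin has no defined meaning for the grade, so the hypothesis in 11.2 is left without a test. And a statement that the dressing is not worse than the stent could be published without showing how the stent side did.

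**Working it through.** **Inputs from section 11.2.** Patency p = 0.85 on both sides, q = 1 − p = 0.15, margin 0.25, one-sided α = 0.05 (z = 1.645), power 80% (z = 0.842), n = 28. The within-patient correlation ρ of patency is not stated; I take 0 to 1 as an assumption.

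**Step 1: reproduce the plan's figure.**
n = 2pq(z_α + z_β)² / margin² = 0.255 × (1.645 + 0.842)² / 0.0625 = 25.2, so 26. The paired form at ρ = 0 gives the same. The stated 28 is within two patients of this. Allowing 6% for complications and failed sinusotomy, 28 / 0.94 = 29.8, so 30. The sample size is therefore a calculation on binary patency, not on the three-level grade.

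**Step 2: how often both openings are closed.**
- P(both closed) = q² + ρpq
- P(both open) = p² + ρpq
- P(one of each) = 2pq(1 − ρ)

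At p = 0.85, pq = 0.1275:

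| ρ (assumed) | Both closed | Of 28 patients | Both open | One of each | Closed pairs as share of concordant pairs |
|---|---|---|---|---|---|
| 0 | 2.25% | 0.6 | 72.25% | 25.5% | 3.0% |
| 0.5 | 8.6% | 2.4 | 78.6% | 12.75% | 9.9% |
| 0.8 | 12.45% | 3.5 | 82.45% | 5.1% | 13.1% |
| 1 | 15.0% | 4.2 | 85.0% | 0% | 15.0% |

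At lower patency, which is an assumption and not a figure from the documents, both openings are closed in 9% to 30% of patients at p = 0.70 (2.5 to 8.4 of 28) and in 25% to 50% at p = 0.50 (7 to 14 of 28).

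**Step 3: does lower patency by itself make the margin easier to meet?**
Normal approximation, equal true patency on both sides, n = 28: chance = Φ(0.25 / √(d/28) − 1.645), with d = 2pq(1 − ρ).

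| Patency | ρ = 0 | ρ = 0.5 | ρ = 0.8 |
|---|---|---|---|
| 85% | 83.5% | 98.0% | > 99.9% |
| 70% | 65.4% | 89.3% | 99.8% |
| 50% | 58.9% | 84.2% | 99.4% |

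Within each column the chance falls as patency falls. Across each row it rises with correlation. At ρ = 0.8 and 50% patency, 45% of patients would have both sides closed and the margin would still almost always be met. Meeting it therefore does not show that the openings stayed open. But it is the correlation that makes it easy to meet, not the failure.

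**The case against.** **The problem is small on the plan's own figure.** This stands. At 85% patency most concordant pairs are both open. Section 1.1 does say "surgical treatment of the frontal sinus has been shown to be more challenging with higher rates of recurrent sinus disease", but it also says that polyp cases respond well to surgery overall, and it gives no rate of late bilateral closure. With no primary visit fixed, 12-month recurrence may not bear on the primary result at all if day 14 is the visit that counts.

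**Absolute measures are already planned.** This stands in part. Opening size, scarring, edema and roof view would partly reveal joint failure, and size is judged against the same 4 mm suction used at entry. It would be too strong to say that the trial cannot answer its objective, which is also worded as a comparison. But no readable text uses these measures to interpret a 'same' grade, and none of them is the quantity in 11.2.

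**The grade concerns overall appearance.** Two closed openings can still differ in scarring or edema, so not every both-closed pair would be graded 'same'. The percentages above bound the ambiguity; they do not predict the grades. Nor does any readable text say that a high share of 'same' grades would establish non-inferiority.

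**A stronger reading: failure on both sides itself pushes towards the favourable conclusion.** A reader might infer this by setting 85% patency at ρ = 0 (25.5% discordant) beside an assumed 60% at ρ = 0.5 (2 × 0.24 × 0.5 = 24% discordant). That changes two things at once. At equal correlation, discordance nearly doubles: 25.5% against 48% at ρ = 0, and 12.75% against 24% at ρ = 0.5. At ρ = 0 the chance of meeting the margin falls from 83.5% to about 60%. The reading is not supported.

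**A figure in 11.3 is not shown.** It follows the primary outcome and may hold grading or analysis detail. The point rests on the readable text.

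**Conclusion.** The point holds as a mismatch between outcome and hypothesis. The trial is sized on patency per side, patency is recorded, and the readable outcome list omits it. So the 11.2 hypothesis has no test, and 'same' is ambiguous between success and failure on both sides.

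The ambiguity covers about 2% to 15% of patients if 85% patency is right, over an assumed correlation of 0 to 1. It becomes large only if patency is well below 85%, which the documents do not state.

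A reader might also infer that the favourable conclusion should depend on the stent-side confidence interval including 85%. The documents do not support such a rule. Section 11.2 gives 85% as a historical rate for frontal sinusotomy in general, so reaching it would not confirm a stent effect. The rule would also be lenient: 20 of 28 patent (71%) would still pass on an exact 95% interval.

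**What to change.** In section 11.3:

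1. List the blinded reviewers' patency (yes/no) for each opening as an outcome, with its definition fixed in advance. Report the paired two-by-two table (both open, stent side only, dressing side only, both closed). Give the paired difference with its one-sided 95% confidence limit against the 25-point margin of 11.2, naming the interval method beforehand. With about 28 × 0.255 = 7 discordant pairs or fewer expected under the plan's assumptions, the choice of method matters.
2. Report the 'same' grades split into both patent, one patent and neither patent, at the visit or visits used for the primary grade. Show stent-side patency with its confidence interval beside any statement that the dressing is not worse.

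The full table is needed, not the difference alone, because a both-closed pair contributes zero to a paired difference just as a both-open pair does.

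The cost is one more secondary outcome and one cross-table, from assessments that section 2.1 already plans. Treatment, visits and sample size do not change.
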